4.4.1 Demographics

Demographic variables to be summarized for the ITT population include:

- Age;
- Sex;
- Ethnicity;
- Race;
- Height;
- Weight.

4.4.2 Severe Alcoholic Hepatitis

Baseline sAH characteristics to be summarized for the ITT population include:

- Steroids >6 weeks prior to baseline (Yes/No); response to steroid treatment (Yes/No/Unknown);
- Steroids during the 6 weeks prior to baseline (Yes/No); response to steroid treatment (Yes/No); and method used to assess response;
- Selected medical treatments at baseline (steroids, pentoxifylline, N-acetyl-cysteine);
- MELD score with corresponding components (creatinine, total bilirubin, and INR);
- Maddrey score with corresponding components (prothrombin time [PT], laboratory control PT, and total bilirubin);
- Subjects that had dialysis at least twice in the past week
- Time from last alcohol consumption to hospital admission (weeks); and
- Time from hospital admission to Randomization (days).

4.4.3 Liver Disease Characteristics

Baseline liver disease characteristics to be summarized for the ITT population include:

- Presence of ascites;
- Liver size;
- Liver volume;
- White blood cell count;

- Child-Pugh Score.

4.4.3.1 Child-Pugh Score

The Child-Pugh score is based on total bilirubin, serum albumin, prothrombin time, ascites, and hepatic encephalopathy; each of these variables is scored from 1 to 3, with 3 indicating the most severe derangement. Details for how to calculate the Child-Pugh score are displayed in Table 1.

Table 1. Child-Pugh Score

| Measure | 1 point | 2 points | 3 points |
|---|---------------------------|--|---------------------------|
| Total bilirubin, mg/dL | <2 mg/dL | 2 to 3 mg/dL | >3 mg/dL |
| Serum albumin ^[1] , g/dL | >3.5 g/dL | 2.8 to 3.5 g/dL | <2.8 g/dL |
| Prothrombin time, prolongation ^[2] , seconds or INR | < 4.0 seconds or < 1.7 | 4.0 to 6.0 seconds or 1.7 – 2.3 (inclusive) | > 6.0 seconds or > 2.3 |
| Ascites ^[3] | none | mild | moderate to severe |
| Hepatic encephalopathy | none | Grade I to II | Grade III to IV |

^[1] If subjects are missing albumin values before Randomization, then use the first available value after Randomization.

^[2] Prothrombin time (PT) prolongation = PT – Control PT. If subjects are missing PT values before Randomization, INR values will be used.

^[3] If ascites is recorded as having more than one severity per subject, choose the more severe category. Only include medical records that are ongoing at Randomization.

The data reported for each of these five variables are collected at baseline and will be the data that will be used to calculate each subject’s baseline Child-Pugh Score. Subjects with a total score of 5 to 6 points will be assigned to Child-Pugh Class A, subjects with a total score of 7 to 9 will be assigned to Child-Pugh Class B, and subjects with a total score of 10 to 15 will be assigned to Child-Pugh Class C. The number of subjects with Child-Pugh Class A, B, and C cirrhosis will be summarized for each treatment group. Difference between treatments will be analyzed using a Chi-squared test.

4.4.4 Clinical Profile

Baseline clinical profile characteristics to be summarized for the ITT population include:

- Kidney (creatinine);
- Cerebral (HE grade);
- Coagulation (INR);
- Circulation (MAP);
- Lungs (pulse oximetry and FiO₂);
- CLIF-SOFA score;
- Systemic Inflammatory Response Syndrome (SIRS).

4.4.4.1 *CLIF-SOFA Score*

The sequential organ failure assessment (SOFA) was modified to take into account specific features of cirrhosis and is called the CLIF-SOFA score (Moreau et al. 2013). The CLIF-SOFA Score consists of subscores ranging from 0 to 4 for each of six components (liver, kidneys, brain, coagulation, circulation and lungs) with higher scores indicating more severe organ impairment (Table 2). If subjects were administered any medications relating to dopamine, dobutamine, terlipressin, epinephrine or norepinephrine at the time of the calculation of the CLIF-SOFA score, then the reason for the administration of the medication will be reviewed by the Medical Monitor in order to establish whether the administration of the medication is pertinent to the determination of the subject’s CLIF-SOFA score for circulation.

The CLIF-SOFA score will be summarized for each treatment group.

Table 2. CLIF-SOFA Score

| Organ System | 0 | 1 | 2 | 3 | 4 |
|--|-------|---------------|---|--|--|
| Liver (bilirubin, mg/dL) | <1.2 | ≥1.2 to <2.0 | ≥2.0 to <6.0 | ≥6.0 to <12.0 | ≥12.0 |
| Kidney (creatinine, mg /dL) | <1.2 | ≥1.2 to <2.0 | ≥2.0 to <3.5 | ≥3.5 to <5.0 | ≥5.0 |
| Cerebral (HE grade) | No HE | I | II | III | IV |
| Coagulation (INR) | <1.1 | ≥1.1 to <1.25 | ≥1.25 to <1.5 | ≥1.5 to <2.5 | ≥2.5 |
| Circulation (MAP, mm Hg) | ≥70 | <70 | Dopamine ≤5* or dobutamine or terlipressin | Dopamine >5 or E≤0.1 or NE ≤0.1* | Dopamine >15 or E>0.1 or NE>0.1* |
| Lungs SpO ₂ /FiO ₂ ¹ | >512 | >357 to ≤512 | >214 to ≤357 | >89 to ≤214 | ≤89 |

Abbreviations: E, epinephrine; FiO₂, fraction of inspired oxygen; HE, hepatic encephalopathy; NE, norepinephrine; and SpO₂, pulse oximetric saturation.

Note: Aggregated scores range from 0 to 24 and provide information on overall severity. Text in bold indicates the diagnostic criteria for organ failures.

*Adrenergic agents administered for at least 1 h (doses are given in µg/kg/min).

¹ If baseline FiO₂ scores are missing, the value 0.21 will be used.

4.4.4.2 *Systemic Inflammatory Response*

Systemic inflammatory response syndrome (SIRS) is defined as two or more of the following variables being present concurrently:

- Fever of more than 38°C (100.4°F) or less than 36°C (96.8°F);
- Heart rate of more than 90 beats per minute;
- Respiratory rate of more than 20 breaths per minute;
- Abnormal white blood cell count (>12,000/µL or <4,000/µL).

The numbers of subjects with SIRS at baseline will be summarized for each treatment group.

4.4.5 Past Medical History

Liver medical history and general medical history will be captured and the terms will be coded using MedDRA, version 18.1. Medical history will be summarized by system organ class and preferred term by treatment group in the ITT population. Subjects with more than one medical history term in the same system organ class or preferred term will only be counted once.

5 DATABASES

Data will be collected in the Electronic Data Capture (EDC) system and other databases for the statistical analyses presented in this plan. The following table lists these databases and provides a description of the type of data being captured in each:

| Data Source | Primary Utility |
|-------------------------------|--|
| VTL-308 clinical database | Primary database for establishment of outcomes. Primary source of screening information, baseline characteristics, laboratory values, concomitant medications, adverse events (AEs), PEth lab results, ELAD Specialist data, and Home Health Care visit data. |
| VTL-308E interim data | Extension data documenting survival (at 6, 9, 12, and 24 months), transplant, incidence of cancer, and quality of life. Survival data earlier than 6 months may also be available for subjects who do not complete their Day 91 visit. Note: a snapshot of the VTL-308E database will be conducted at the time of the VTL-308 database lock to provide the updated information for the analysis of the primary endpoint of overall survival. |
| ELAD System performance files | Information recorded automatically by the ELAD System (Sorin S3/S5) documenting multiple system performance parameters during subject treatment. These data are stored in CSV format (one file per subject/cartridge set). |
| Manufacturing data | Files documenting ELAD cartridge performance and product release parameters such as albumin, transferrin, glucose consumption, and oxygen utilization, along with date of manufacture, and date of shipping. |

6 GENERAL ANALYSIS CONSIDERATIONS

If significant OS differences are identified between populations, then subgroup analyses of OS will be summarized for additional populations.

6.1 EFFICACY

- Log-rank analysis of the effect of ELAD on OS will be used;
- Chi-squared test of the effect of ELAD on proportions of survivors will be used at Study Days 28 and 91.

6.2 SAFETY

- A t-test or ANOVA test will be used for selected continuous variables;
- Fisher's exact test or Chi-squared test will be used for categorical variables.

7 EFFICACY ANALYSIS

Unless otherwise specified, all analyses will be of randomized subjects by treatment group.

No data imputation will be used, except for the ECBL and Lille analyses. For the primary log-rank analyses of the effect of ELAD on OS, the subject's last available study evaluation through Day 91 after the calendar date at which the last subject was randomized will be used. This OS follow-up will draw from data generated by VTL-308 and VTL-308E follow-up data. Every effort will be made to capture the survival status of each randomized subject through Day 91 after the calendar date at which the last subject was randomized.

For the log-rank analysis of the effect of ELAD on OS, the null hypothesis will be that the true survival curves do not differ and will be tested at the two-sided 0.05 level of significance. The primary efficacy analysis will be carried out on the ITT population, and sensitivity analyses will be performed using the mITT, PP and Safety populations. Kaplan-Meier estimates of survival will be generated for both treatment groups, and estimates will be obtained for median survival, 25th and 75th quartiles. A Cox regression analysis will be performed to obtain an estimate of the hazard ratio and corresponding confidence limits. Exploratory analyses of treatment effect within subgroups will be performed.

7.1 PRIMARY EFFICACY ANALYSIS

7.1.1 Overall Survival (OS) of Subjects with sAH through at least Study Day 91

OS will be assessed using a log-rank analysis of survival data in the intent-to-treat (ITT) population. Protocol VTL-308E will provide additional survival data up to a maximum of 5 years. Kaplan-Meier estimates of survival will be provided, along with estimates of median survival, 25th and 75th quartiles, by treatment group, while a Cox regression analysis will be used to provide estimates of the hazard ratio and its confidence limits. These analyses will also be carried out on the mITT, Per-Protocol (PP) and Safety populations as sensitivity analyses.

In addition, a similar sensitivity analysis for 91-day overall survival will be carried out using overall survival data through Day 91. Subjects who survived at Day 91 are censored at Day 91. Subjects who were lost to follow-up prior to Day 91 are censored at their last contact Study Day.

Although every effort will be made to determine each subject's survival status through the calendar date for the primary analysis of OS, it is possible that some subjects will be lost to follow-up. In the primary OS analysis, such observations will be censored as of the last date when the subject's survival status was known.

7.1.2 Subgroup Analyses of OS

Descriptive summaries will be provided to give evidence regarding estimates of treatment effect across subgroups defined by standard demographics, selected baseline characteristics, medical history, regional and geographical site-related factors and baseline standard of care (SOC). These descriptive summaries will provide evidence regarding the generalizability of the primary analyses of treatment effect. The ITT population will be used in these descriptive summaries, which are listed below.

- Demographics and baseline characteristics:
 - Age (<Median and ≥Median);

- Gender;
- Baseline MELD score (<Median and ≥Median);
- Hepatic encephalopathy grade (0 vs 1 or 2 vs 3 or 4);
- Baseline total bilirubin level (<Median and ≥Median);
- Baseline creatinine (<Median and ≥Median);
- Baseline INR;
- Region (US vs. Non-US).
- Medical history characteristics:
 - Time from hospital admission for this episode of sAH to Randomization (<Median and ≥Median).
- Other Baseline measures:
 - Site size:
 - This will be evaluated based on defining high-enrolling sites as those that enroll 4 or more subjects, and low-enrolling sites as those that enroll fewer than 4 subjects, and presenting summary statistics for OS within each of these subgroups;
 - The same analysis will be done with 8 or more subjects as a cut-off.
 - All sites with only one subject enrolled will be combined together and compared to all sites;
 - Any site with more than 10% of the total number of subjects will be analyzed separately and compared to all sites.
 - Enrollment order within a site. This will be evaluated based on defining early-enrolled subjects as those subjects who were the first or second subject enrolled within a site compared to later-enrolled subjects who will be defined as those subjects who were at least the third or later subject enrolled within a site; summary statistics for OS within each of these subgroups will be presented.

The above factors were identified as potential effect modifiers for the effect of ELAD, based on scientific considerations including the outcomes of the VTI-208 Study, the STOPAH study (Thursz et al. 2015) and the findings of the EASL-CLIF consortium (Arroyo et al. 2015, Moreau et al. 2013).

7.1.3 Cox Regression Analyses of OS

In exploratory analyses, the estimated effect of treatment on OS will be adjusted for baseline factors that are strongly prognostic for OS and that could be imbalanced across treatment groups in spite of randomization. In the first step of these exploratory analyses, each covariate will be assessed in a univariate analysis to assess its prognostic influence. In the second step, the 5 most prognostic covariates will be entered into a Cox multivariate regression model along with treatment to obtain an estimated effect of treatment on OS, adjusted for these covariates.

The following factors will be included in these analyses:

- Age (continuous; dichotomized based on median);
- Baseline MELD score (continuous; dichotomized based on median);
- Baseline total bilirubin level (continuous; dichotomized based on median);
- Baseline PT ratio (continuous);
- Baseline white blood cells (continuous);
- Baseline blood urea nitrogen (BUN) (continuous);
- Baseline creatinine (continuous);
- Hepatic encephalopathy (0, 1/2, 3/4);
- Steroids use (Yes/No);
- Baseline weight (continuous; dichotomized based on median);
- Baseline height (continuous; dichotomized based on median);
- Region (USA vs. Europe).

Other baseline factors may also be identified and included in exploratory analyses related to OS.

Study site characteristics will also be examined to see if region, site size, or enrollment order have an effect on OS between treatment groups. Hazard ratios will be displayed as well as p-values from univariate cox regression models including the study site characteristic, treatment group, and site characteristic by treatment group interaction.

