7.1.4 Assessment of Potential Bias due to Treatment Group Assignment

VTL-308 is an open-label study. While every effort has been made in the study protocol to minimize the effects of post-treatment differences in investigator evaluation, medical care and subject behavior, there is a potential that differences in these factors may be associated with treatment group assignment, and that these differences might influence outcomes. An evaluation of the proportion of survivors at Study Days 28 and 91 will be carried out to determine whether these differences had any impact on study outcome. Parameters assessed will include, but not be limited to, the following:

- Alcohol use post-discharge. This will be evaluated based on either a PEth result of >20 ng/mL (evidence of moderate or heavy alcohol consumption) or any self-report of alcohol use post-discharge (note: a positive PEth result will supersede a self-report of no alcohol use);
- Length of Initial ICU Stay (<Median and ≥Median), defined as the first ICU discharge date minus ICU admission date plus 1, if the admission date is after randomization. If the admission date is before randomization, then the length of stay will be the discharge date minus randomization date plus 1. If the discharge date is missing and the subject died, the death date will be used;
- Length of Initial Hospital Stay (<Median and ≥Median), defined as the hospital discharge date minus randomization date plus 1. If discharge date is missing and the subject died, the death date will be used;
- Steroids Use Post-randomization (Yes/No);
- Steroids Use Post-randomization for <7 days (Yes/No);

- Steroids Use Post-randomization for ≥ 7 to < 14 days (Yes/No);
- Steroids Use Post-randomization for ≥ 14 to < 28 days (Yes/No);
- Steroids Use Post-randomization for at least 28 days (Yes/No);
- Concomitant heparin use within the first 10 days of the study (Yes/No);
- For the ELAD group only, ELAD treatment duration dichotomized based on < 72 hours vs. ≥ 72 hours. This analysis will be based on total ELAD treatment duration inclusive of any time off treatment (i.e., final stop date/time of treatment, defined as the time at which the ultrafiltrate pump is switched off for the last time – initial start date/time of treatment, defined as the time at which the ultrafiltrate pump is switched on for the first time). Additional analyses of ELAD treatment duration are described in [Section 8.2](#) and [8.10.1](#).

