7.3.3 Outcome Relative to Selected Screening Factors

In addition, exploratory analyses of outcome relative to selected screening factors will be conducted. The overall survival rates at Study Day 28 and Study Day 91 for the ELAD treatment group and the Control group will be provided for the following subgroups:

- Steroid / pentoxifylline / NAC use at Randomization (Yes/No);
- Steroid / pentoxifylline / NAC use during treatment period (Yes/No);
- Steroid / pentoxifylline / NAC use after treatment (Yes/No).

For the ELAD subjects, treatment period is defined as the period from initiation of ELAD treatment to ELAD treatment stopping. For the Control subjects, treatment period is defined as the period from Study Day 2 to Day 7.

7.3.4 Early Change Bilirubin at Different Levels at Study Day 7

In order to further explore the change in bilirubin as a potential surrogate endpoint for studies of new therapeutic approaches to the treatment of sAH, together with findings from VTI-208 that significant differences were observed for all ECBL values between ECBL 10% and ECBL 40% in the Safety population in the VTI-208 study (VTL data on file), additional exploratory analyses will be carried out. The proportion of subjects will be presented by treatment group and by the following bilirubin categories for the Safety and ITT Populations. Differences between treatment groups at each cutoff will be evaluated using a Chi-squared test.

- 0% reduction from baseline in bilirubin (ECBL0);
- 10% reduction from baseline in bilirubin; (ECBL10);
- 15% reduction from baseline in bilirubin; (ECBL15);
- 25% reduction from baseline in bilirubin. (ECBL25);
- 30% reduction from baseline in bilirubin. (ECBL30);
- ECBL as a continuous variable (use median as cutoff).

Furthermore, exploratory analyses will be carried out and the proportion of survivors at Study Days 28 and 91 will be presented by achieving bilirubin reduction (Yes vs No for ECBL0, ECBL10, ECBL15, ECBL20, ECBL25, ECBL30) for overall, ELAD treatment group and Control group using the ITT Population.

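### Does choosing the five adjustment covariates by a screen on the trial's own survival data undermine the exploratory Cox model in SAP 7.1.3?

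*SAP*

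**What the plan says.** SAP 7.1.1 makes the log-rank test in the ITT population the primary analysis. It adds a Cox hazard ratio for which no covariates or strata are named.

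SAP 7.1.3 then adds an exploratory estimate, adjusted for baseline factors that "could be imbalanced across treatment groups in spite of randomization". First, "each covariate will be assessed in a univariate analysis to assess its prognostic influence". Then "the 5 most prognostic covariates will be entered into a Cox multivariate regression model along with treatment".

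Twelve candidates are listed: age, MELD, total bilirubin, PT ratio, white cells, BUN, creatinine, encephalopathy, steroid use, weight, height and region. Age, MELD, bilirubin, weight and height each appear with two codings, as in the entry "Baseline MELD score (continuous; dichotomized based on median". The steroid entry reads only "Steroids use (Yes/No". A closing sentence allows further baseline factors in exploratory analyses. The other Cox models in the section examine site characteristics and their interaction with treatment. They do not adjust the overall effect.

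**The concern.** An adjusted estimate is most useful when only one answer is possible. Here three choices are left open: the statistic that ranks the factors, the coding of five of them, and the timing of steroid use. MELD also competes with bilirubin and creatinine, two of its own components, so one piece of prognostic information can take several of the five places.

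The steroid item looks the most awkward. SAP 4.4.2 has three pre-randomisation versions, one of them "Steroids during the 6 weeks prior to baseline (Yes/No". SAP 7.1.4 has five post-randomisation versions, starting with "Steroids Use Post-randomization (Yes/No". SAP 7.3.3 has three combined versions, such as "Steroid / pentoxifylline / NAC use at Randomization (Yes/No". Adjusting for a post-randomisation version would mean adjusting for something that treatment may have influenced.

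At stake is whether the sponsor could show a convenient adjusted hazard ratio in support of the primary result, or to soften it. A fixed model with a few named covariates would seem to close this off at no cost.

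**Working it through.** **Design figures.** SAP 1.3 gives 90% power at a hazard ratio of 0.417 with 55 deaths and 0.447 with 65. Under Schoenfeld's formula with 1:1 allocation and two-sided 0.05, HR = exp(-2(1.960 + 1.282)/√d):
- d = 55: exp(-6.484/7.416) = 0.417
- d = 65: exp(-6.484/8.062) = 0.447
- d = 60: exp(-6.484/7.746) = 0.433, used below as a mid-range effect

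**Size of the open choice.** Five factors from 12 can be chosen in 792 ways, and two codings of five factors give 2^5 = 32 patterns. Five single-parameter covariates plus treatment make six parameters, so 55/6 = 9.2 to 65/6 = 10.8 deaths per parameter. The model is not overloaded.

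**Two codings compared.** Inputs from SAP 1.3: 75 per arm, uniform accrual over 720 days, cut at 720 + 91 = 811 days, 10% loss, control one-year survival 48%. Assumed, because the documents do not give them: covariate distributions and correlations, and a prognostic log-hazard SD of 0 to 0.7. One reading codes everything as continuous. The other uses the median split wherever the SAP offers it. Both rank by univariate chi-square.
- At HR 0.433 the two readings choose the same five factors in 21-50% of trials.
- Their adjusted hazard ratios differ by a median of 3-7%. With SE(log HR) about 0.28, that is ln(1.03)/0.28 = 0.11 to ln(1.07)/0.28 = 0.24 standard errors. In one trial in ten the difference is at least 9-19%, or 0.3-0.6 standard errors.
- They disagree on p < 0.05 in 2.7-3.5% of trials.
- Null rejection (10,000 trials per setting, Monte Carlo SE 0.2-0.3 points): log-rank 4.9-5.4%, fixed age and MELD model 5.2-5.4%, either screening reading alone 5.6-5.9%, the more favourable of the two 6.6-7.2%.

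**Nine readings compared.** A separate simulation (3,000 trials per effect, about 60 deaths) crossed three ranking rules with three coding rules and set them against one fixed five-covariate model.

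| | HR 1 | HR 0.65 | HR 0.417 |
|---|---|---|---|
| Fixed model rejects | 5.9% | 37.6% | 89.2% |
| Any single reading rejects | 5.8-7.3% | 34.1-37.5% | 86.2-89.1% |
| At least one of nine rejects | 10.1% | 44.5% | 91.6% |

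Within a trial, the largest of the nine hazard ratios exceeded the smallest by a median of 11-14%. Ranking by univariate likelihood-ratio p-value with continuous coding gave 5.8% under the null, against 5.9% for the fixed model (Monte Carlo SE √(0.059 × 0.941/3000) = 0.4 points).

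**Would a fixed model be better?** In further runs at HR 0.433, a fixed age and MELD model gained about 1-4 points of power over the screen when those two factors carried the prognosis. It lost about 3-7 points when white cells, BUN and encephalopathy did.

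**Overlap with MELD.** If five factors were drawn at random, MELD would enter with at least one of bilirubin, creatinine or PT ratio (the candidate nearest to INR) with probability (5/12) × (1 - 70/330) = 33%. Under the continuous reading the simulated figure for MELD with a component is 37-98%. The low end is near chance. The high end depends on giving MELD much of the prognosis.

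**Steroid timing.** SAP 7.1.3 opens by restricting adjustment to baseline factors, and the sentence that permits additions speaks of other baseline factors. That rules out the SAP 7.1.4 items, which are explicitly post-randomisation. The missing baseline prefix tells us little, since age, encephalopathy and region lack it too. The choice left is among the pre-randomisation items in SAP 4.4.2.

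**The case for a change.** The best case for a change is that the Protocol (section 2) promises exploratory factors prespecified in the SAP, and SAP 1.2.3 says they are. The trial is open-label, the sponsor sees each assignment (Protocol 5.3.2) and shares data management (SAP 9). Randomisation is 1:1 at site level (SAP 2), with no prognostic stratification described, so chance imbalance among 150 subjects is plausible. The sponsor also holds the VTI-208 data, from which a short list could be justified. Fixing the model costs only wording.

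Part of this stands. Ranking, coding and the steroid definition are missing, the list can be extended, and analytic freedom deserves more care in an open-label trial. But the factors themselves are listed in advance, as promised. The number five is fixed, and selection is on prognosis, not on the treatment contrast. The 10.1% figure needs someone to fit nine models and report whichever is significant, in either direction. In favour of ELAD alone it is 5.0%, against 2.8-3.7% for a single reading.

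Nor is a fixed age and MELD list clearly better. Eligibility confines age to 18-49 and MELD to below 30 (Protocol 4.3 and 4.4), and the documents do not show that these remain the strongest predictors within that range. Screening a listed set is a fair response to that uncertainty.

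**Conclusion.** The plan can stand. Screening on the trial's own outcomes, which looks like the main fault, does little harm under a reading settled in advance: 5.6-5.9% null rejection against 5.2-5.4% for a fixed age and MELD model in one simulation, 5.8-7.3% against 5.9% for a fixed five-covariate model in the other. Replacing the screen with age and MELD is a trade-off of a few points of power in either direction.

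What remains is missing detail in an exploratory model. An analyst has to settle one ranking statistic, one coding per factor and one pre-randomisation steroid definition before the programs can run, and ordinary choices give nearly the same operating characteristics. The primary log-rank test, its alpha, the sample size and the Cox hazard ratio in SAP 7.1.1 are unaffected, and that hazard ratio will be available beside any adjusted one.

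Two conditions attach. The simulated sizes rest on assumed covariate distributions and prognostic strengths. The conclusion also assumes that the adjusted estimate keeps its exploratory label, with the reading chosen without sight of the treatment result.
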